4.2.3. Additional estimands

To examine the sensitivity of the results of primary analysis to departures from the assumption that Intercurrent Events (IEs) did not occur, treatment policy strategy will be used to IEs of study treatment discontinuation not related to the COVID-19 pandemic, the on- and off- treatment data will be included in the analyses.

Supplemental estimand 1:

The estimand is described by the following attributes:

- Population: Chinese participants with severe eosinophilic asthma.
- Treatment condition: mepolizumab 100mg SC given every 4 weeks compared to placebo every 4 weeks, both treatments given on top of standard of care. Further details on standard of care can be found in Section 6.
- Variable: number of clinically significant exacerbations over 52 weeks.
- Summary measure: rate ratio of exacerbations between the mepolizumab arm and placebo.
- Intercurrent events:
 - Study treatment discontinuation
 - Related to the COVID-19 pandemic: hypothetical strategy
 - Not related to the COVID-19 pandemic: treatment policy strategy

Handling of Missing Data:

Missing data will be imputed differently depending on the handling strategy for the specific intercurrent event.

- Missing data due to hypothetical strategy for intercurrent event of study treatment discontinuation (data collected after the occurrence of the IE will be excluded from the analysis), assuming that missing data is missing at random (MAR).
- Missing data due to study withdrawal. Study withdrawal before the completion of the study will create missing outcome data. This may occur concurrently or after the IE. The assumptions used to impute the missing part of the data for subjects who withdraw early from study will be as follows:
 - a) Missing at Random (direct likelihood). Using the negative binomial model assumes that missing data is missing at random (MAR). The missing data will be imputed conditional upon the subjects own observed number of events, which are not missing, based on the negative binomial generalized linear model with offset variable.
 - b) Missing at Random (multiple imputation). Using an underlying negative binomial model, post-withdrawal counts were imputed conditional upon the subject's own observed number of events prior to withdrawal.
 - c) Jump to Reference. Missing counts will be imputed conditional upon the subjects own observed number of events prior to withdrawal. The impact of sampling from this conditional distribution is that if their event rate prior to withdrawal is worse than would be expected (positive residual) on mepolizumab, their imputed event rate after withdrawal will be worse than the expected event rate on placebo. Missing data in the placebo arm are imputed under randomised-arm MAR.

4.2.4. Supplementary Analyses

- As a supportive analysis to enable comparability of results with global MEA115588 study, the primary analyses may be repeated using the “Per-protocol” analysis population (see Section 6.2.13 for the definition).

- Impact of the Prior Weight of the robust mixture prior.

Another supportive “tipping point” type of analysis will be conducted to assess the impact on the results of different prior weights given to the historical data in the robust mixture prior for primary endpoint.

The prior weights of the informative global component of the prior will be varied from 0 to 1 in the increment of 0.05 and the primary analysis will be repeated for each value of the weight. When the prior weight is 0 or 1, the mixture prior will become a normal distribution thus the Bayesian diagram will be the standard conjugate analysis.

The posterior mean, median and 90% credible interval of the posterior distribution will be reported for each prior weight, along with the probability that true rate ratio is less than 1 (equivalent to the log rate ratio being less than 0)

4.3. Secondary Endpoint(s) Analyses

4.3.1. Key secondary endpoint(s)

- Time to first clinically significant exacerbations.
- Mean change in St. Georges Respiratory Questionnaire (SGRQ) at Week 52
- Frequency of clinically significant exacerbations requiring hospitalization (including intubation and admittance to an ICU) or ED visits over the 52-week treatment period
- Frequency of clinically significant exacerbations requiring hospitalization over the 52-week treatment period
- Mean change from baseline in clinic pre-bronchodilator FEV1 at Week 52

Definition of endpoint(s)/estimands

The principle of Estimand consideration for each key secondary endpoint is to keep a similar Estimand strategy for intercurrent events with study MEA115588, since it is a bridging study. To test the sensitivity of the results of the main estimand for key secondary endpoints, the supplemental estimand for these endpoints are defined in Section 4.3.2.

Endpoint(s)
• Time to first clinically significant exacerbation
Estimand

The estimand is described by the following attributes:
 
 • Population: Chinese participants with severe eosinophilic asthma

Endpoint(s)

 • Treatment condition: mepolizumab 100mg SC given every 4 weeks compared to placebo every 4 weeks, both treatments given on top of standard of care. • Variable: Time to first clinically significant exacerbations. • Summary measure: Rate of first clinically significant exacerbation. Comparison between the mepolizumab arm and placebo will be assessed through the hazard ratio. • Intercurrent events: 
 ◦ Study treatment discontinuation - hypothetical strategy 
The handling strategy for the IEs of discontinuation of study intervention will be based on a hypothetical approach; specifically, the effects estimated will be under the hypothetical scenario where the IE did not occur. If a subject discontinues study treatment without any clinically significant exacerbations, the subject will be censored at the date of study treatment discontinuation which assumes censoring at random.

Endpoint(s)

 • Mean change in St. Georges Respiratory Questionnaire (SGRQ) at Week 52
Estimand

The estimand is described by the following attributes:
 
 • Population: Chinese participants with severe eosinophilic asthma • Treatment condition: mepolizumab 100mg SC given every 4 weeks compared to placebo every 4 weeks, both treatments given on top of standard of care. • Variable: 
 ◦ Mean change in St. Georges Respiratory Questionnaire (SGRQ) at Week 52. • Summary measure: 
 ◦ LS Mean change in St. Georges Respiratory Questionnaire (SGRQ) between the mepolizumab arm and placebo. • Intercurrent events: 
 ◦ Study treatment discontinuation- hypothetical strategy 
The handling strategy for the IEs of discontinuation of study intervention will be based on a hypothetical approach; specifically, the effects estimated will be under the hypothetical scenario where the IE did not occur.

Endpoint(s)

 • Mean change from baseline in clinic pre-bronchodilator FEV1 at Week 52
Estimand

The estimand is described by the following attributes:
 
 • Population: Chinese participants with severe eosinophilic asthma • Treatment condition: mepolizumab 100mg SC given every 4 weeks compared to placebo every 4 weeks, both treatments given on top of standard of care. • Variable: 
 ◦ Change from baseline in clinic pre-bronchodilator FEV1 at Week 52 • Summary measure: 
 ◦ Mean change from baseline in clinic pre-bronchodilator FEV1. Comparison between the mepolizumab arm and placebo will be assessed with the mean difference.

Endpoint(s)

 • Intercurrent events: 
 ○ Study treatment discontinuation-hypothetical strategy 
The handling strategy for the IEs of discontinuation of study intervention will be based on a hypothetical approach; specifically, the effects estimated will be under the hypothetical scenario where the IE did not occur.

Endpoint(s)

 • Frequency of clinically significant exacerbations requiring hospitalization (including intubation and admittance to an ICU) or ED visits over the 52-week treatment period • Frequency of clinically significant exacerbations requiring hospitalization over the 52-week treatment period
Estimand

The estimand is described by the following attributes:
 
 • Population: Chinese participants with severe eosinophilic asthma • Treatment condition: mepolizumab 100mg SC given every 4 weeks compared to placebo every 4 weeks, both treatments given on top of standard of care. • Variable: 
 ○ Number of clinically significant exacerbations requiring hospitalization (including intubation and admittance to an ICU) or ED visits over 52 weeks. ○ Number of clinically significant exacerbations requiring hospitalization over 52 weeks. • Summary measure: 
 ○ Rate ratio of clinically significant exacerbations requiring hospitalization (including intubation and admittance to an ICU) or ED visits between the mepolizumab arm and placebo. ○ Rate ratio of clinically significant exacerbations requiring hospitalization between the mepolizumab arm and placebo • Intercurrent events: 
 ○ Study treatment discontinuation-hypothetical strategy 
The handling strategy for the IEs will be the same with primary estimand defined in Section 4.2.1

4.3.2. Main analytical approach

Time to first clinically significant exacerbations

Endpoint / Variables

 • Time to first clinically significant exacerbations
Model Specification

 • Cox's proportional hazards model • Terms in the model:

Endpoint / Variables

 Response: time to first on-treatment, clinically significant exacerbation Categorical: treatment group, baseline maintenance oral corticosteroids (OCS vs no OCS) Continuous: baseline disease severity (as % predicted FEV1), number of exacerbations in the year prior to the study (as an ordinal variable (2, 3, 4+))
Model Checking & Diagnostics

 The proportional hazards assumption will be examined by obtaining the Kaplan-Meier estimates of the survival function $S(t)$ over time separately for each treatment group. In addition, the $\ln \{-\ln[S(t)]\}$ plot will be produced.
Model Results Presentation

 Hazard ratios and the percent reduction in risk of a first exacerbation at any time on-treatment during the study for the pairwise treatment comparisons with associated 95% CIs and p-values will be presented. The probability of having an on-treatment clinically significant exacerbation at week 16, 32 and 52 and 95% CI for each treatment group will be presented.
Sensitivity and Supportive Analyses

 As a supportive analysis, the analysis will be repeated using the “Per-protocol” analysis population.
Additional estimands

A supplementary analysis will be performed using the “treatment policy” strategy for the intercurrent event of discontinuation of treatment. This analysis will include both on-treatment and off-treatment clinically significant exacerbation data from subjects who withdraw from treatment prior to W52. Exacerbations will be included provided the exacerbation onset date is before week 52. Participants that have not experienced a clinically significant exacerbation on or before the end of study date/early withdrawal/lost to follow up study/ date of death day are censored at the end of study date/early withdrawal/date of death.

SGRQ at Week 52

Endpoint / Variables

 Mean change in St. Georges Respiratory Questionnaire at Week 52 
Details for how to score the SGRQ are outlined in the SGRQ manual (Mar, 2016).

Model Specification

 MMRM Analysis performed using a mixed models repeated measures analysis (MMRM) adjusting covariates: baseline, baseline maintenance OCS therapy (OCS vs. no OCS), exacerbations in the year prior to the study (as an ordinal variable), baseline

Endpoint / Variables
% predicted FEV1, treatment and visit, plus interaction terms for visit by baseline and visit by treatment group

 • A dataset om_dataset will be constructed to reflect the data structure of no missing observations, i.e. had each subject been reported with the same visits.
Model Results Presentation

 • Least-square (LS) means and LS mean change from baseline values for each treatment group will be presented with their associated standard errors as well as 95% CIs. The estimated treatment difference along with corresponding standard error, 95% CI for each Week will be presented. • The treatment differences (and associated 95% CIs) at week 52 will also be presented graphically.
Missing data imputation
The analysis using the MMRM model assumes that missing data is missing at random (MAR).
Sensitivity and Supportive Analyses

 • To compare with MEA115588 results, a sensitivity analysis will be analysed by analysis of covariance (ANCOVA) with covariates of baseline, baseline maintenance OCS therapy (OCS vs. no OCS), exacerbations in the year prior to the study (as an ordinal variable), baseline % predicted FEV1, and treatment. In this sensitivity analysis, the mean score for a subject at either timepoint (i.e. baseline or exit visit) will only be calculated if at least 75% of the questions were answered. If fewer than 75% of the questions were answered then the mean score for that subject at that timepoint will be considered missing. Only the observed data will be used and no imputation will be done for missing data. • Another sensitivity analyses of the MMRM will be performed using multiple imputation methods based on pattern mixture models. • A supportive analysis will be repeated using the “Per-protocol” analysis population • Another supportive analysis will be performed by domain: Symptoms domain, Activity domain and Impacts domain
Additional estimands
A supplementary analysis will be performed using the “treatment policy” strategy for the intercurrent event of discontinuation of treatment. This analysis will include both on-treatment and off-treatment value. For missing data imputation, the missing data are assumed as MAR.

Clinically significant exacerbations requiring hospitalization/ ED visits and clinically significant exacerbations requiring hospitalization

Endpoint(s)

 Frequency of clinically significant exacerbations requiring hospitalization (including intubation and admittance to an ICU) or ED visits over the 52-week treatment period Frequency of clinically significant exacerbations requiring hospitalization over the 52-week treatment period
Model Specification, Checking & Diagnostics, Results, Presentation

 These endpoints will be analyzed using the same methodology as the primary analysis of Frequency of clinically significant exacerbations in Section 4.2.1.
Missing data imputation
The analysis using the negative binomial model assumes that missing data is missing at random (MAR).
Sensitivity and Supportive Analyses

 As a supportive analysis, the analysis will be repeated using the “Per-protocol” analysis population.
Additional estimands
The same additional estimand and similar methods for missing data imputation will be used as the primary endpoint in Section 4.2.3.

Pre-bronchodilator FEV1 at Week 52

Endpoint / Variables

 Mean change from baseline in clinic pre-bronchodilator FEV1 at Week 52
Model Specification

 Mixed Models Repeated Measures (MMRM) model. Change from baseline in pre-bronchodilator FEV1 will be analyzed using a mixed models repeated measures analysis (MMRM) adjusting covariates of baseline, baseline maintenance OCS therapy (OCS vs. no OCS), exacerbations in the year prior to the study (as an ordinal variable), treatment and visit, plus interaction terms for visit by baseline and visit by treatment group. A dataset om_dataset will be constructed to reflect the data structure of no missing observations
Model Results Presentation

 Least-square (LS) means and LS mean change from baseline values for each treatment group will be presented with their associated standard errors as well as 95% CIs. The estimated treatment difference along with corresponding standard error, 95% CI for each Visit will be presented.

Endpoint / Variables

 The LS mean treatment differences (and associated 95% CIs) for all visits will also be presented graphically.
Missing data imputation
The analysis using the MMRM model assumes that missing data is missing at random (MAR).
Sensitivity and Supportive Analyses

 The sensitivity analyses of the repeated measures analyses will be performed for the FEV1 key secondary endpoint using multiple imputation methods under MAR based on pattern mixture models. The method is analogous to the multiple imputation of exacerbation events. A supportive analysis of the repeated measures pre-bronchodilator FEV1 analysis will be performed, excluding all values captured within 6 hours of a SABA being administered or 12 hours of a LABA being administered to the subject. Another supportive analysis will be repeated using the “Per-protocol” analysis population
Additional estimands
A supplementary analysis will be performed using the “treatment policy” strategy for the intercurrent event of discontinuation of treatment. This analysis will include both on-treatment and off-treatment value. For missing data imputation, the missing data are assumed as MAR.

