Complete electronic Case Report Form (eCRF)	X	X	X	X	X	X	X	X	X	X	X	X	X	X	X	X	X	X	X	X	X	X	X	X	
eDiary dispense and training		X ¹⁸																							
eDiary review			X			X	X	X	X	X	X	X	X	X	X	X	X	X	X			X		X	
eDiary collection																						X		X	
Dispense paper worksheet		X	X			X	X	X	X	X	X	X	X	X	X	X	X	X	X						
Collect/review paper worksheet			X			X	X	X	X	X	X	X	X	X	X	X	X	X	X	X		X		X	
Dispense Rescue Salbutamol		X	X			X	X	X	X	X	X	X	X	X	X	X	X	X	X						
Collect Used Rescue Salbutamol			X			X	X	X	X	X	X	X	X	X	X	X	X	X	X	X		X		X	

1. The pre-screening visit (Visit 0) can occur on the same day as the screening visit (Visit 1) but must be completed prior to initiating any Visit 1 procedures.
2. Visit 2 can occur 1 to 4 weeks after Visit 1. Results from Visit 1 procedures must be available for review of randomization criteria.
3. Only those patients attending the PK sub-study will perform the visit. . Protocol amendment 4 updated Study Day of V2-1 (from day 7 to day 8) and V2-2 (from day 14 to day15) to clarify the duration of PK sample collection. On final PK Sample ID form and related PK CRF forms in InForm System, “VISIT 2 PREDOSE” refers to “VISIT2 DAY1”, “VISIT 2 DAY7” refers “VISIT 2 DAY8”, and “VISIT 2 DAY 14” refers to “VISIT 2 DAY15” in SoA.
4. Informed consent for the optional PK sub-study must be obtained before collecting a related sample.
5. Parasitic screening is only required in subjects who have visited high-risk countries in the past 6 months. Sites should use local laboratories.
6. Only required if results from a chest x-ray or CT-scan, taken within the past 6 months, is not available
7. Reversibility test is required at screen. If subject does not reverse \geq 12% and 200 mL in FEV1 at visit 1 (screen), the procedure may be repeated at Visit 2.
8. A comprehensive physical exam should be conducted. See Section 7.3.1 for specific details of the comprehensive physical exam.
9. A brief physical exam should be conducted. See Section 7.3.1 for specific details of the brief exam.
10. During the treatment period, all lab samples (not applicable for PK samples) and procedures should be obtained pre-dose.

11. Differential results including eosinophil counts will be blinded from Visit 3 onwards.
12. Urine pregnancy testing is only required for females of child bearing potential. An assessment must be made at baseline to determine child bearing potential of each female study participant (see [Table 6](#)).

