5.1. Inclusion Criteria

A subject will be eligible for inclusion in this study only if all of the following criteria apply:

1. **Informed Consent:** Able to give written informed consent prior to participation in the study, which will include the ability to comply with the requirements and restrictions listed in the consent form. Subjects must be able to read, comprehend, and write at a level sufficient to complete study related materials.
2. **Age and Weight:** At least 12 years of age at Visit 0 and a minimum weight of 40 kg.
3. **FEV1:** Persistent airflow obstruction as indicated by:
 - For subjects ≥ 18 years of age at visit 1, a pre-bronchodilator FEV₁ $< 80\%$ predicted normal values calculated by Quanjer reference equations [[Quanjer, 2012](#)]
 - For subjects 12-17 years of age at visit 1:
 - A pre-bronchodilator FEV₁ $< 90\%$ predicted ([Quanjer, 2012](#)) recorded at Visit 1 OR
 - FEV₁: FVC ratio < 0.8 recorded at visit 1
4. **Eosinophilic information:** Prior documentation of eosinophilic asthma or high likelihood of eosinophilic asthma as per Randomization Criteria 1.
5. **Inhaled Corticosteroid:** Regular treatment with high dose inhaled corticosteroid (ICS) in the 12 months prior to Visit 1, of which at least 9 months accumulated documented is required, the 3 months prior to Visit 1 is mandatory. With or without maintenance oral corticosteroids(OCS)*.
ICS dose must be ≥ 500 mcg/day fluticasone propionate (FP) or equivalent daily (for ICS/LABA combination preparations, Seretide 50/250 mcg bid and above or equivalent will meet this ICS criteria). *[Maintenance OCS is defined as a prescribed regimen of a minimum average daily dose of prednisone 5mg (or equivalent)].
6. **Controller Medication:** Current treatment with one or more additional controller medication, besides ICS. At least one additional controller medication must have

been regularly used for at least 3 months prior to Visit 1. [e.g., long-acting beta-2-agonist (LABA), leukotriene receptor antagonist (LTRA), or theophylline]

7. **Exacerbation history:** Previously confirmed history of two or more exacerbations requiring treatment with systemic CS (intramuscular (IM), intravenous, or oral), in the 12 months prior to Visit 1, despite the use of high-dose ICS. For subjects receiving maintenance CS, the CS treatment for the exacerbations must have been a two-fold increase or greater in the dose for at least 3 days is required.

8. **Gender:** Male or Female

Female participants:

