7.2.4. Pulmonary Function Testing including Reversibility

Spirometry will be conducted, using the site's own equipment at the visits specified in the Schedule of Activities (Section 1.2). The spirometer should meet American Thoracic Society standards and produce a printout of all data generated, which should be stored in the subject's notes. The spirometer should be calibrated in accordance with the manufacturer's instructions and a calibration log maintained. Spirometry must be performed at the same time (± 2 hour) of the Visit 2 spirometry. Subjects should try to withhold SABAs or SAMAs for ≥ 6 hours and LABAs for ≥ 12 hours prior to clinic visit, if possible. Assessments to be recorded will include FEV₁, FVC. Pre-bronchodilator measurements will be taken at each clinic visit. In addition, at visit specified in the Schedule of Activities (Section 1.2) post-bronchodilator values will be recorded following standard reversibility testing. For subjects unable to achieve $\geq 12\%$ reversibility and 200 mL change at Visit 1, reversibility can be repeated at Visit 2. Further details of spirometry and reversibility testing procedures are presented in the Study Reference Manual.

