9.4.1.2. Key Secondary Analyses

- Time to first clinically significant exacerbations.
- Mean change in St. Georges Respiratory Questionnaire at Week 52
- Frequency of clinically significant exacerbations requiring hospitalization (including intubation and admittance to an ICU) or ED visits over the 52-week treatment period
- Frequency of clinically significant exacerbations requiring hospitalization over the 52-week treatment period
- Mean change from baseline in clinic pre-bronchodilator FEV1 at Week 52

Time to first clinically significant exacerbations will be analysed using Cox’s proportional hazards model with covariates of treatment group, baseline maintenance OCS therapy, number of exacerbations in previous year (as an ordinal variable), baseline disease severity (as % predicted FEV1).

St. Georges Respiratory Questionnaire (SGRQ) score will be analysed using mixed repeated measures model adjusting for baseline maintenance OCS therapy, baseline SGRQ, number of exacerbations in previous year (as an ordinal variable), baseline % predicted FEV1, and treatment and visit, plus interaction terms for visit by baseline and visit by treatment group.

The secondary endpoints of rate of exacerbations requiring hospitalization (including intubation and admittance to an ICU) or ED visits and rate of clinically significant exacerbations requiring hospitalization will be analyzed using negative binomial regression, as described for the primary endpoint above.

Pre-bronchodilator FEV1 will be analyzed using mixed effects repeated measures model adjusting for baseline maintenance OCS therapy, baseline FEV1, number of exacerbations in previous year (as an ordinal variable), and treatment, and visit, plus interaction terms for visit by baseline and visit by treatment group.

The point estimate as well as the estimate of the variability in above analyses will be provided. More details will be provided in full RAP.

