4.1.2. Baseline Definition

For all endpoints (except as noted in baseline definitions) the baseline value will be the latest pre-dose assessment with a non-missing value, including those from unscheduled visits. If time is not collected, Day 1 assessments are assumed to be taken prior to first dose and used as baseline.

For data collected via the eDiary device (i.e. morning peak flow, usage of rescue medication (i.e. salbutamol/albuterol), asthma symptom score and frequency of awakening due to asthma symptoms), the baseline for analyses of averaged 4-weekly data will be calculated using values from the run-in period as shown in Section 4.2 in protocol.

Parameter	Study Assessments can be Considered as Baseline			Baseline Used in Data Display
	Screening	Day -6 to Day 1	Day 1 (Pre-Dose)	
[Efficacy]				
Salbutamol/albuterol use		X		Average of measurements from Day -6 to Day 1 pre-dose
Asthma symptom scores		X		Average of measurements from Day -6 to Day 1 pre-dose
Awakening at night		X		Average of measurements from Day -6 to Day 1 pre-dose
Morning PEF		X		Average of measurements from Day -6 to Day 1 pre-dose
[Safety]				
12-Lead ECG	X			Screening

Unless otherwise stated, if baseline data is missing no derivation will be performed and baseline will be set to missing.

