6.1.2. Demographic and Baseline Characteristics

Demography

Demographic characteristics (age, sex, ethnicity, race, height, weight and body mass index) will be summarised and listed. For age group, it also will be categorised by group: 12-17 years, 18-29 years, 30-49 years, 50-64 years and ≥ 65 years.

Randomization stratification factor

Randomization stratification factor blood eosinophil count at screening (≥ 300 cells/ μL and < 300 cells/ μL) will be presented by treatment group. A shift table of differences between stratification factor and as Randomized (data entered into the IWRS system) will be produced.

Stratification factors (randomized and actual strata) will be listed for all subjects by treatment group.

Medical Conditions

The proportion of subjects who report medical conditions in each medical condition class will be presented, for current and past conditions separately. Current and past medical conditions will be listed.

Cardiovascular Assessment

A summary of the baseline cardiovascular assessment will be presented. The proportion of subjects who report a family history of medical conditions that may indicate predisposition towards cardiovascular conditions will be summarised.

Asthma History and Tobacco Use

Asthma history including duration of asthma (including derived age of onset), OCS use and exacerbations in the 12 months prior to Visit 1 will be summarised and listed.

Asthma disease characteristics and causes of exacerbations will be summarised and listed.

History of tobacco use will be summarised (i.e., non-smoker, former smoker).

Screening and Baseline Lung Function Tests

The following Screening (Visit 1) and (Visit 2) clinic lung function results will be summarised. Pre and post bronchodilator FEV1 will be listed in the same listing as the raw FEV1 listing in Section 4.3.2. The rest of the screening lung function results detailed below will be listed in a separate listing.

- Pre and post bronchodilator FEV1 (mL)
- Pre and post-bronchodilator percent predicted FEV1 (%)
- Reversibility (in mL and in %)
- Pre and post bronchodilator Forced Vital Capacity FVC (mL)
- Pre and post bronchodilator FEV1/FVC

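### The Week 52 FEV1 model adjusts for one pre-dose FEV1 reading; adding the Visit 1 reading would probably narrow the confidence interval (about 0–12% in SE, under assumed correlations)

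*SAP*

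**What the plan says.** **Model.** SAP 4.3.2 analyses change from baseline in pre-bronchodilator FEV1 with an MMRM "adjusting covariates of baseline, baseline maintenance OCS therapy (OCS vs. no OCS), exacerbations in the year prior to the study (as an ordinal variable", followed by treatment, visit, visit-by-baseline and visit-by-treatment. Protocol 9.4.1.2 has the same structure: "adjusting for baseline maintenance OCS therapy, baseline FEV1, number of exacerbations in previous year (as an ordinal variable), and treatment, and visit", plus the same interactions. OCS use and exacerbation history are in the model, but there is a single FEV1 term.

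**Baseline.** SAP 4.1.2 sets the general rule that "the baseline value will be the latest pre-dose assessment with a non-missing value, including those from unscheduled visits". For FEV1 that is normally Visit 2.

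**The other reading.** Protocol 7.2.4 states that "Pre-bronchodilator measurements will be taken at each clinic visit". Protocol 7.1.2 and 7.1.3 list lung function among the critical procedures at both Visit 1 and Visit 2, and the Schedule of Activities marks spirometry at both. Inclusion Criterion 3 in protocol 5.1 ("Persistent airflow obstruction as indicated by") is judged on screening spirometry, for adults and adolescents alike. The Schedule of Activities also notes that "Visit 2 can occur 1 to 4 weeks after Visit 1".

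**Use of Visit 1.** SAP 6.1.2 reports both readings descriptively: "The following Screening (Visit 1) and (Visit 2) clinic lung function results will be summarised". Visit 1 FEV1 is in neither the main FEV1 model nor any FEV1 sensitivity, supportive or supplementary analysis listed in SAP 4.3.2.

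**The concern.** One spirometry reading is a noisy measure of a subject's usual FEV1, and the documents give reasons to expect noise. Protocol 7.2.4 uses each site's own spirometer and asks for bronchodilators to be withheld only where possible. SAP 4.3.2 plans a supportive analysis that drops readings taken too soon after a SABA or LABA.

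A second reading, one to four weeks earlier and also before randomisation, can account for some of the variation in Week 52 FEV1 that the first leaves unexplained. Leaving it out may make the confidence interval wider than it need be.

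Precision matters here because the planned output for FEV1 is an estimated difference with its standard error and 95% CI. The endpoint has no multiplicity-controlled test, and the plan specifies a MEA115588 prior only for the log exacerbation rate ratio, so nothing is borrowed for FEV1.

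**Working it through.** **The plan's own figures.** There is none to reproduce for FEV1: no SD, target difference, power or between-visit correlation is stated. The sizing in protocol 9.2.1 concerns exacerbations. It does reproduce: with 128 per arm, rates 1.7 and 1.02 and dispersion 0.8, the variance of the log rate ratio is (1/1.7 + 1/1.02 + 2×0.8)/128 and the power is 90.1% against a stated 90%. It says nothing about FEV1.

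**Approach.** I treat the Week 52 contrast from an unstructured MMRM with visit-by-baseline as an ANCOVA at Week 52. This is an approximation when there is drop-out. Because the Visit 2 value is a covariate, analysing change from Visit 2 or the Week 52 value itself gives the same treatment difference and residual variance.

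Let r2 and r1 be the correlations of Week 52 FEV1 with Visits 2 and 1, and r12 the correlation between Visits 1 and 2. All are assumed. As a fraction of the outcome variance:

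- Residual variance with Visit 2 only: 1 − r2².
- Ratio of residual variances after adding Visit 1: 1 − (r1 − r12·r2)² / [(1 − r12²)(1 − r2²)].
- If all three equal r, the two-reading residual is 1 − 2r²/(1 + r), and the ratio reduces to (1 + 2r)/(1 + r)².

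**Equal correlations.**

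| r | Visit 2 only | Both readings | Variance ratio | SE reduction | Equivalent N (from 300) |
|---|---|---|---|---|---|
| 0.5 | 0.750 | 0.667 | 0.889 | 5.7% | 337 |
| 0.6 | 0.640 | 0.550 | 0.859 | 7.3% | 349 |
| 0.7 | 0.510 | 0.424 | 0.830 | 8.9% | 361 |
| 0.8 | 0.360 | 0.289 | 0.802 | 10.4% | 374 |
| 0.9 | 0.190 | 0.147 | 0.776 | 11.9% | 387 |

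**Visits 1 and 2 closer to each other than to Week 52.**

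| r12 | r2 | r1 | Variance ratio | SE reduction | Equivalent N (from 300) |
|---|---|---|---|---|---|
| 0.90 | 0.80 | 0.80 | 0.906 | 4.8% | 331 |
| 0.85 | 0.75 | 0.72 | 0.944 | 2.8% | 318 |
| 0.90 | 0.80 | 0.77 | 0.964 | 1.8% | 311 |
| 0.90 | 0.80 | 0.72 | 1.000 | none | 300 |

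The third row by hand: (0.77 − 0.72)² / (0.19 × 0.36) = 0.0025/0.0684 = 0.0365, so the ratio is 0.9635 and its square root 0.982. In the last row r1 = r12·r2, so Visit 1 adds nothing once Visit 2 is known.

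**Entry selection.** Subjects enter partly because Visit 1 FEV1 is low, which narrows its range. I simulated 300 subjects under equal correlations of 0.6, 0.7 and 0.8. Without selection the variance ratios were 0.863, 0.834 and 0.805. Keeping only subjects whose standardised Visit 1 value was below 0.5 (an illustrative cut) gave 0.915, 0.886 and 0.852, which are SE reductions of 4.3%, 5.9% and 7.7%. The gain shrinks but remains.

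**Bias.** Both readings precede randomisation and selection on Visit 1 acts equally on both arms. In a linear model, adding a pre-randomisation covariate leaves the target mean difference unchanged.

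**The case against.** The strongest objection is that the single-baseline model is deliberate and consistent. Protocol and SAP agree on it. SAP 4.1 wants models similar to those of MEA115588, SAP 4.3.1 repeats the principle for the key secondary estimands, and SAP 4.2.2 explains that even the stratification factor is left out of the primary model for consistency. So the choice does buy something: comparability.

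That stands as a reason to keep the current model available, but not as a reason to exclude the other. SAP 4.1 asks for similarity unless otherwise specified, and the SAP has already solved the same problem for SGRQ: MMRM is the main analysis and an ANCOVA is kept as a sensitivity analysis for comparison with MEA115588.

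A second objection, that the gain could be small, also stands:

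- Protocol 7.2.4 ties the clock time of spirometry to Visit 2, so Week 52 should be better matched to Visit 2 than to Visit 1.
- Protocol 4.1 and randomisation criterion 6 in protocol 5.3 require a return to baseline asthma status for at least a week before Visit 2 after a run-in exacerbation. That criterion sets no such rule for Visit 1.
- Inclusion Criterion 3 truncates Visit 1.

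Each of these argues against taking the equal-correlation table at face value. A reader might infer from it a guaranteed gain of at least 3%. The documents do not support that floor, since it requires Visit 1 to predict Week 52 as well as Visit 2 does.

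A reader might also tie the point to the plan's account of reduced information. That account (protocol 9.2.1) concerns a lower exacerbation rate and higher dispersion, and implies nothing about FEV1 precision.

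**Conclusion.** The point holds as one of efficiency. The FEV1 model uses one of two pre-randomisation readings that should be available for every eligible subject, and adding the other would probably narrow the interval for the Week 52 difference. The supportable size is about 0–12% off the standard error. The upper end needs equal between-visit correlations near 0.9; the lower end applies if Visit 1 carries no information beyond Visit 2. All correlations are assumed, and entry selection pulls the gain down.

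A reader might go further and conclude that the planned FEV1 estimate is biased, that its interval is invalid, or that the primary result is affected. None of these follows. The current model is valid and consistently specified, no type I error issue arises, and the exacerbation analysis is untouched. The change is worth making because it is cheap, but the trial's conclusions do not depend on it.

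**What to change.** Before unblinding, in the pre-bronchodilator FEV1 part of SAP 4.3.2:

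- Add Visit 1 pre-bronchodilator FEV1 and its interaction with visit as covariates.
- Keep change measured from the baseline of SAP 4.1.2 (normally Visit 2).
- Retain the current single-baseline MMRM as a sensitivity analysis for comparability with MEA115588.
- State the rule for any subject with only one pre-dose reading. Under SAP 4.1.2 a missing Visit 2 value makes Visit 1 the baseline, so both covariates would then hold the same number.
- Record the change in SAP 4.9, which now declares no departures from protocol amendment 4.

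A lighter alternative is to leave the main model alone and list the two-reading model as a supportive analysis. That avoids changing the protocol's main model.

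**Cost.** No new data are needed. The interaction uses one extra coefficient per post-baseline spirometry visit, collinear with visit-by-baseline, in an unstructured-covariance model that already has a convergence fallback in SAP 6.3. That is tolerable with 300 subjects. The other cost is a documented departure from the covariate list in protocol 9.4.1.2.
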